Patients with low and medium risk of PCa assessed by PSAD+PI-RADS score clinical diagnostic model cannot benefit directly from this study. However, the clinical information and samples provided by patients will help to verify the accuracy and clinical application of the clinical diagnostic model of PSAD+PI-RADS score, so as to obtain a more effective method of PCa diagnosis, which is the common interest of all PCa-related patients.

For patients with a high risk of PCa assessed by the PSAD+PI-RADS score clinical diagnostic model for radical prostatectomy without prostate biopsy, the benefits include: ①to avoid complications of prostate biopsy; ②to avoid the economic burden caused by prostate biopsy and the psychological and physical burden caused by prostate biopsy; ③to avoid the possibility of tumor spread after prostate biopsy; ④to avoid the possibility of repeated prostate biopsy; ⑤to avoid the risk of developing PCa in the future.

(2) Risk

The main risk in this study is the risk of performing biopsy-free radical prostatectomy. It is possible that the clinical diagnostic model of PSAD+PI-RADS score is evaluated as high risk and PSMA/PET-CT examination is positive, but the postoperative pathology indicates the possibility of non-malignant tumor, which

indicates that the prostate organ without tumor will be removed.

(3) Risk/benefit assessment

For patients undergoing biopsy-free radical prostatectomy, the doctor will fully inform the patients and their families of the relevant information and risks before the operation. The postoperative pathology of the patient suggests that it is a malignant tumor, and the patient effectively avoids the related risks caused by prostate biopsy. The postoperative pathology suggests that the patient is non-malignant, and the patients with high risk evaluated by PSAD+PI-RADS score clinical diagnostic model and positive PSMA/PET-CT examination are still at high risk of prostate cancer, and they have a great risk of developing prostate cancer, which required regular follow-up and even repeated prostate biopsy, and finally could not avoid the treatment of radical surgery, which is a great burden and injury to the patients themselves. Biopsy-free radical prostatectomy can effectively reduce the risk of prostate cancer in high-risk groups, decrease the physical and psychological burden of patients, and the benefits outweigh the risk. In addition, the construction of a prostate cancer diagnosis model suitable for the Chinese population can be beneficial to early screening, early diagnosis, and early treatment of prostate cancer, reduce the proportion of patients with advanced prostate cancer, improve the survival rate of patients, and reduce the consumption of medical resources and unnecessary prostate biopsies.

15、Reference

[4] Mottet N, van den Bergh RCN, Briers E, et al. EAU-EANM-ESTRO-ESUR-SIOG Guidelines on Prostate Cancer-2020 Update. Part 1: Screening, Diagnosis, and Local Treatment with Curative Intent[J]. *Eur Urol*. 2021; 79(2):243-262.

[6] Duffy MJ. Biomarkers for prostate cancer: prostate-specific antigen and beyond[J]. *Clin Chem Lab Med*. 2020; 58(3):326-339.

Annex II. Annual implementation plan

December 2022-August 2023: Fifty-seven patients who met the requirement of radical prostatectomy without prostate biopsy are enrolled in the group. The basic personal and clinical information of the patients are recorded in detail.

September 2023-December 2023: We will collate all data, statistical analysis, article writing and contribution.

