power is 80%. The required number of positive samples (positive results in PSMA combined model) is 55. Considering the drop rate of 5%, the study is expected to enroll 57 patients.

The negative samples are all the patients in the study who are negative in the PSMA combined model and should perform prostate biopsy.

Analysis set

- 1) Full analysis set (FAS): the set of patients determined according to the intention to treat, which refers to the data set of all patients who participated in this study.
- 2) Per protocol set (PPS): refers to the completed trial and excludes patients who seriously violate the scheme (patients violate the selection criteria or exclusion criteria, etc.).
- 3) Security data set (SS): all the patients who participated in this study and conducted at least once safety assessment constitute the security population of this study.

Primary endpoint analysis

The primary endpoint of this study is the positive predictive value of PSMA combined model for the diagnosis of csPCa. For the analysis of the primary endpoints, the results of both FAS and PPS will be taken into account. The positive predictive value of PSMA combined model for csPCa diagnosis and its 95% confidence interval (95%CI) will be recorded. When the lower limit of 95%CI is greater than the target value, it is considered that the detection rate of PSMA combined model is up to the standard, which can be used as a proof for a new clinical treatment scheme called biopsy-free radical prostatectomy.

Secondary endpoint analysis

	
No target value is set for the secondary endpoint, and only the detection rate and 95%CI are calculated at the time of evaluation.
 
Safety endpoint analysis
 
The severity, quantity and incidence of AE, ADR and SAE and their correlation with overall trial, examination or operation and patients are statistically and descriptively analyzed.

Expected duration	12 months

1、Background

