Definition: The patients with positive results of PSMA combined model and pathological examination accounted for the proportion of all patients with positive results of PSMA combined model.

Calculation method: Positive predictive value= $\frac{\text{true positive}}{\text{true positive}+\text{false positive}} \times 100\%$

6.3) Secondary effectiveness index

1) Misdiagnosis rate

Definition: The patients with positive results of PSMA combined model and negative results of pathological examination accounted for all patients with positive results of PSMA combined model.

Calculation method: Misdiagnosis rate= $\frac{\text{false positive}}{\text{true negative}+\text{false positive}} \times 100\%$

7. Safety evaluation

The severity, quantity and incidence of AE, ADR, and SAE and their correlation with overall trial, examination or operation and individual patients are statistically and descriptively analyzed.

(2) Study flow

1). Study flow chart

[figure not shown]

Table 1 The schedule of the screening period, perioperative period, and evaluation period for this trial.

Items	Screening period (-7~0 days)	Perioperative period of radical prostatectomy (1- 14 days)	Evaluation period
Demographic data	▲		
Signs and symptoms	▲		
Completed the blood test ^a and mpMRI examination	▲		
Evaluation by the online diagnostic model	▲		
Signing of informed consent forms	▲		
¹⁸ F-PSMA-1007 PET/CT examination ^b	▲		
Enrollment	▲		
Radical prostatectomy ^c		▲	

Reading of pathological slices			▲
Follow up and adverse events	▲	▲	▲

^a Prostate cancer marker test (Serum total PSA).

^b The researchers decide whether an ¹⁸F-PSMA-1007 PET/CT examination is performed based on the results of the risk probability by online diagnostic model evaluation.

^c The researchers decide whether the radical prostatectomy is performed based on the decisions of the patients and their relatives. Full preoperative communication is needed.

mpMRI, multi-parameter magnetic resonance imaging; ¹⁸F-PSMA-1007 PET/CT, ¹⁸F-prostate-specific membrane antigen-1007 positron emission tomography/computed tomography; PSA, prostate specific antigen.

2). Screening period (-7~0 day)

The following process will be completed during the screening period:

- Allocation of patient's number;
- Collection of demographic information (age, place of origin, height, weight, and healthy condition, etc.);

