This study is designed for a single group of objective performance criteria. With reference to the opinions of many senior clinical experts and statistical experts, it is considered that the clinically acceptable positive predictive value should not be less than 90%. According to the literature exploration and previous research results, it is expected that the positive predictive value of PSMA combined model is more than 98%. Suppose the significance level is 0.05 (bilateral) and the degree of power is 80%. The required number of positive samples (positive results in PSMA combined model) is 55. Considering the drop rate of 5%, the study is expected to enroll 57 patients.

2). Statistical analysis set

- 1) Full analysis set (FAS): the set of patients determined according to the intention to treat, which refers to the data set of all patients who participated in this study.
- 2) Per protocol set (PPS): refers to the completed trial and excludes patients who seriously violate the scheme (patients violate the selection criteria or exclusion criteria, etc.).
- 3) Security data set (SS): all the patients who participated in this study and conducted at least once safety assessment constitute the security population of this study.

3). Principle of statistical analysis

- 1) IBM SPSS (version 25.0) statistical software is used for statistical analysis.
- 2) All statistical tests use two-sided tests, and a P value of less than 0.05 will be considered to be statistically significant normally.
- 3) Description statistics: the measurement of continuous variables is described by means, standard deviation, and median, interquartile range; categorical variables are described by number and proportion (%).
- 4) The comparison of the two groups of variables will be analyzed by appropriate methods according to the type of variables. T-test or Wilcoxon rank sum test is used to compare measurement indexes between groups. χ^2 test or Fisher exact test is used to compare categorical variables between groups.

4). Group completion status

The selection and completion of the cases are described respectively, and the corresponding statistical analysis of the population is summarized and listed by the enrollment, drop, elimination, completed cases, and the number of cases of each analysis set.

5). Equilibrium analysis of baseline data

Baseline analysis based on full data set (FAS)

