The number of patients enrolled in the group, the number of completions, and the total drop rate are described respectively, and the list of excluded cases and the detailed list of unfinished reasons are listed. The baseline features of the patients are statistically described.

6). Evaluation indexes

The analysis of effectiveness indexes is based on the full analysis set (FAS) and the per-protocol set (PPS) and is described in the table below.

Table 2 Statistical analysis of main indicators ^f

		Results of pathological diagnosis		total
		positive	negative	
PSMA combined model	positive	A	B	A+B
	negative	C	D	C+D
		total	A+C	B+D
				N=A+B+C+D

Positive predictive value (true positive rate)= $A/(A+B) \times 100\%$;

Misdiagnosis rate= $B/(A+B) \times 100\%$.

6.1) Main effectiveness indexes

The most important effectiveness index of this study is the positive predictive value (true positive rate) of PSMA combined model, which is the proportion of the positive results of postoperative pathological diagnosis to all enrolled patients. For the analysis of the primary endpoint, the results of both FAS and PPS will be considered. The positive predictive value of PSMA combined model for csPCa diagnosis and its 95%

CI will be calculated, when the lower limit of 95%CI is greater than the set target value, it is considered that the detection rate of PSMA combined model is up to the standard, which can be used as a proof for a new clinical treatment scheme called biopsy-free radical prostatectomy.

6.2) Secondary effectiveness evaluation index

The secondary endpoint of the study is the detection rate of any-grade PCa (Gleason score $\geq 3+3$) and high grade PCa (hgPCa) (Gleason score $\geq 4+3$) by PSMA combined model, the positive predictive value and misdiagnosis rate of any-grade PCa and hgPCa will be assessed.

Notably, no target value is set for the secondary endpoint indexes, and only the point estimated value and 95% CI are calculated at the time of evaluation.

Safety endpoint analysis

6.3) Safety evaluation

The severity, quantity and incidence of AE, ADR and SAE and their correlation with overall trial, examination or operation and patients are statistically and descriptively analyzed. In addition to the above statistical methods, detailed and additional exploratory analysis may be required and confirmed in the Statistical Analysis Program (SAP).

3、Data management

(1) Raw data verification

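### No review of accumulating specimens without csPCa is tied to the success rule, which by the second false positive (third under Wald) can no longer be met with 57 patients; the stated 80% power is also not delivered

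*Combined protocol and SAP*

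**What the plan says.** **Accrual and analysis.** In Annex II, "Fifty-seven patients who met the requirement of radical prostatectomy without prostate biopsy are enrolled in the group" between December 2022 and August 2023. The entry for September to December 2023 reads "We will collate all data, statistical analysis, article writing and contribution".

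**Success rule.** The target PPV is 90%. The criterion is met "When the lower limit of 95%CI is greater than the target value" (Protocol summary, Primary endpoint analysis), and section 3(1)6.1 repeats it: "when the lower limit of 95%CI is greater than the set target value". Neither place names an interval method. Both FAS and PPS are to be considered, and nothing says which one decides.

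**Denominator.** Section 2(1)6.2 uses true positives over true plus false positives, and the formula under Table 2 in section 3(1)6) is the same, A/(A+B). The prose of section 3(1)6.1 instead speaks of "the proportion of the positive results of postoperative pathological diagnosis to all enrolled patients".

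**Sample size (section 3(1)1)).** The expected PPV is above 98%. "Suppose the significance level is 0.05 (bilateral) and the degree of power is 80" (per cent). This is said to need 55 model-positive patients. "Considering the drop rate of 5%, the study is expected to enroll 57 patients".

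**Harm and oversight.** The Background calls the harm from a false positive irreparable. The Risk paragraph names removal of a prostate without tumour as the main risk. Section 5(4) has the researcher give the ethics committee an opinion on continuing, suspending or terminating the trial after adverse events. Section 8 covers re-consent on important new information, and revision of the scheme when problems arise.

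**The concern.** Each false positive is an irreversible operation on a man without csPCa. The success rule fixes in advance how many such results the trial can absorb, and that number is very small. Once it is exceeded, further operations cannot change the primary conclusion. The text nevertheless states no running count and no review prompted by pathology before the 57th patient.

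The documents do not rule out a PPV below plan. The Background gives the prediction model alone a PPV only above 80% at the 0.60 cut-off. The biopsy-free series it cites is retrospective, with 25 of 25 positive; its exact lower limit is 0.025^(1/25) = 0.863, which is below the 90% target.

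The same small tolerance determines the power. If only one false positive is allowed, the 80% claim has to be checked against that rule.

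**Working it through.** **Inputs.** Target 0.90, planned PPV 0.98, two-sided 0.05, power 80%, 55 evaluable and 57 enrolled (section 3(1)1)); success if the lower 95% limit exceeds 0.90 (section 3(1)6.1); 57 patients in nine months (Annex II). A false positive is any model-positive patient whose pathology is not csPCa (section 2(1)6.1).

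**1. The plan's own figure.** The usual formula is n = [(z_α√(p0q0) + z_β√(p1q1))/(p1−p0)]².
- Two-sided: [(1.96×0.30 + 0.8416×0.14)/0.08]² = (0.7058/0.08)² = 77.8, so 78.
- One-sided: [(1.645×0.30 + 0.1178)/0.08]² = 58.4, so 59.
- Arcsine: 61 two-sided, 48 one-sided.

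None of these gives 55. The two-sided formula comes close only with p1 = 0.99 (55.7), which the plan does not state. On drop-out, 55/0.95 = 57.9, so 57 is one short, which is trivial.

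**2. How many false positives the rule tolerates.** The exact lower limit for x successes in n is the 2.5% quantile of Beta(x, n−x+1). Jeffreys uses Beta(x+½, n−x+½). Wald is p − 1.96√(p(1−p)/n).

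| Result | Exact | Wilson | Jeffreys | Wald |
|---|---|---|---|---|
| 56/57 | 0.906 | 0.907 | 0.921 | 0.948 |
| 55/57 | 0.879 | 0.881 | 0.892 | 0.917 |
| 54/57 | 0.854 | 0.856 | 0.866 | 0.889 |

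For a fixed number of failures the limit rises with n. Two failures are first tolerable at n = 70 (exact), 69 (Wilson) or 62 (Jeffreys), and three under Wald at n = 64. All exceed 57, so the second false positive (third under Wald) settles the matter whenever it occurs. It can be settled sooner: under exact limits one false positive passes at 53/54 (0.901) but fails at 52/53 (0.8993).

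**3. Power under that rule at PPV 98%.**
- Exact, Wilson or Jeffreys, at most one false positive: n = 57 gives 0.98^57 + 57×0.02×0.98^56 = 0.316 + 0.368 = 0.684; n = 55 gives 0.329 + 0.369 ≈ 0.699.
- Wald, at most two: 0.894 at n = 57. The chance of passing at a true PPV of exactly 90% is then 0.067, against the 0.025 implied by a two-sided 0.05. Under the at-most-one rule it is 0.018.

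**4. What a review could avert.** The operation T at which the r-th false positive occurs is negative binomial, truncated at 57. With L further patients operated on before the review takes effect, the expected number of false positives is Σ P(T=t)[r + min(L, 57−t)(1−PPV)] over t ≤ 57, plus Σ k·P(k false positives) for k < r. The documents give no pathology turnaround. I assume L = 6, about one month's accrual (57/9 = 6.3), and show L = 12 as a range. Enrolment is taken to end after the review.

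| True PPV | No review (57×(1−PPV)) | 2nd, L=6 | 2nd, L=12 | 3rd (Wald), L=6 |
|---|---|---|---|---|
| 90% | 5.7 | 2.6 | 3.1 | 3.5 |
| 95% | 2.9 | 2.0 | 2.2 | 2.4 |
| 98% | 1.1 | 1.0 | 1.1 | 1.1 |

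**5. How often the trigger would be reached.** The second false positive comes before patient 57 with probability 0.98, 0.78 and 0.31 at PPV 90%, 95% and 98%.

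**The case against.** **The plan is not without oversight.** A reader might infer that nothing could halt the trial. That goes too far. The SAE definition in section 5(1) includes permanent structural or functional defects and could be read to cover a needless prostatectomy, which would bring in the section 5(4) opinion. Section 8 allows re-consent and revision of the scheme without any adverse event. This stands. What is missing is a link from pathology results to those routes: the graded list in section 5(2) contains complications only. A few pages of the document were not available to me, so I claim absence only for the text I had.

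**Timing of slide reading.** A reader might infer from Annex II that specimens stay unread until the last operation. The documents do not say so. Annex II dates the analysis, and section 2(2)4.2 blinds the readers without fixing when they read.

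**Drop-outs as failures.** Section 3(1)6.1, read literally, would count enrolled patients without pathology as non-successes. Both formulas use A/(A+B), and every enrolled patient is model-positive by inclusion criterion 5, so loose wording is the likelier explanation. I do not rely on the literal reading.

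**Small benefit and reasons to continue.** At 95% the review averts at most about 0.9 specimens, and at 98% about 0.1. It would often be triggered at 95%, a PPV above the level called acceptable. Later patients still inform the PPV estimate, the secondary endpoints and safety. All this stands, and is why the review should not be binding.

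**Conclusion.** The concern holds in limited form. The success boundary can be computed in advance and is reached by the second false positive (exact, Wilson, Jeffreys) or the third (Wald), yet no stated review is tied to it. This assumes that enrolment stops at 57 and that false positives stay in the deciding set. A PPS exclusion for a serious violation could remove one, and the plan does not say whether FAS or PPS decides.

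The expected saving is about three specimens without csPCa at a true PPV of 90%, one or fewer at 95%, and almost none at 98%. It also assumes the stated lag, that the ethics committee then ends enrolment, and that patients not enrolled do not have the same operation elsewhere. These specimens should not be read as tumour-free prostates: Gleason 3+3 cancer counts as a false positive, so the figures are an upper bound on prostates removed without any cancer.

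The power statement is wrong as written and does not depend on the lag. At PPV 98% the power is 68.4% (n = 57) or 69.9% (n = 55) under exact, Wilson or Jeffreys limits. Wald exceeds 80% only by letting the one-sided error rise to 6.7%. The plan should be changed on both counts.

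**What to change.** 1. Name the exact Clopper-Pearson interval for the primary criterion. Keep true positives over true plus false positives, as in section 2(1)6.2 and under Table 2, and align the prose of section 3(1)6.1 with it. State whether FAS or PPS decides.
2. Restate the power in section 3(1)1) as about 68% with 57 and 70% with 55 evaluable patients at PPV 98%. If 80% is to be kept under the exact rule, the smallest evaluable number is 70, which tolerates two false positives (power 83.5%).
3. Add a non-binding statistical futility review. Report consensus pathology as it becomes available, with a stated turnaround, and keep a running count. When success has become arithmetically impossible under the named interval and deciding set, refer the question of continuing enrolment to the ethics committee through the section 5(4) and section 8 routes, and leave the decision to them.

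**Cost.** A paragraph of text, a running count and prompt consensus reading. A review placed at the point of impossibility costs neither power nor alpha, provided it matches the named interval: a review at two under a Wald rule would interrupt trials that could still succeed. The real downside is a less precise PPV estimate if enrolment ends early, and the review would be reached before patient 57 in 31% of trials at the planned PPV and 78% at 95%.
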